Obstructive Sleep Apnea (OSA) is a prevalent condition associated with significant morbidity, including hypertension and cardiovascular disease. Continuous positive airway pressure (CPAP) is the first-line treatment, but adherence is notoriously poor, with long-term compliance as low as 10-20%. For patients intolerant to CPAP, surgical options are offered, yet their long-term success rates average only 30%.

Myofunctional therapy (MFT) addresses the functional dimension of OSA by strengthening oropharyngeal muscles to increase airway stability. A meta-analysis has already demonstrated that MFT alone can reduce the AHI by 50% in adults. The rationale for this study is that surgery primarily addresses static anatomical obstructions, while MFT targets the functional deficit of poor neuromuscular tone that surgery alone cannot correct. We hypothesize that a combined, synergistic approach-where surgery provides anatomical relief and MFT enhances dynamic airway stability-will lead to superior treatment outcomes compared to surgery alone.

4. Study Goals and Objectives

- **Goal:** To determine if adding a structured postoperative MFT program to sleep surgery improves treatment outcomes for patients with moderate-to-severe OSA compared to surgery alone.
- **Primary Objective:**
 - To compare the reduction in AHI at 3 and 12 months post-surgery between the OP+MFT and OP-only groups, with success defined as >50% AHI reduction and a final AHI <20 events/hour.
- **Secondary Objectives:**
 - To compare the change in lowest oxygen saturation (LSaO₂) between the groups at 3 and 12 months.
 - To compare the change in the snore index between the groups at 3 and 12 months.

5. Study Design

This is a prospective, single-surgeon, non-randomized controlled study conducted at a single medical center.

- **Research Population:** Adults aged 20-65 with moderate-to-severe OSA (AHI ≥ 15 events/hour) confirmed by PSG.
- **Inclusion Criteria:**
 - Age 20-65 years.
 - Moderate-to-severe OSA (AHI ≥ 15 events/hour)
 - Friedman palate position grade I-II and tonsil size grade III-IV.
 - Patients who refuse or are unable to tolerate CPAP.
- **Exclusion Criteria:**
 - Central or mixed sleep apnea.
 - BMI $> 27 \text{ kg/m}^2$.
 - Severe cardiopulmonary disease or psychiatric illness.
 - Pregnancy or cancer.
 - Significant weight gain during the follow-up period.

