- **Study Duration:** The project was conducted between January 2020 and January 2024. Each participant's follow-up duration is 12 months.

6. Methodology

- **Interventions:**
 - **Surgery:** All patients will undergo surgery performed by the same surgeon, including uvulopalatopharyngoplasty (UPPP) and adjunctive nasal turbinate reduction surgery.
 - **Grouping:** After surgery, enrolled patients will be divided into two groups based on personal willingness: Group A (OP+MFT) or Group B (OP- only).
 - **Myofunctional Therapy (MFT):** Group A patients will begin a 12-week MFT program starting at the third postoperative week. The program includes:
 - Initial Instruction: Two face-to-face training sessions with a speech-language pathologist in the first week.
 - Home Practice: Twice-daily sessions of 15 minutes each, guided by instructional videos.
 - Exercises: Tongue elevation and protrusion drills, soft palate elevation, pharyngeal wall contractions, and nasal breathing retraining.
 - Supervision: Biweekly review sessions with the therapist to ensure correct performance and adherence.
- **Outcome Measures & Procedures:**

- All participants will undergo overnight polysomnography (PSG) at the sleep center at baseline (pre-surgery), and at 3 and 12 months post-surgery.
- Objective data on AHI, LSaO₂, and snore index will be collected.
- **Study Flow Diagram:** [Eligible OSA Patients] -> [Informed Consent] -> [Baseline PSG] -> [Undergo Surgery (UPPP)] -> [Post-op Group Allocation] ---> [Group A: OP+MFT] -> [12-Week MFT Program] ---> [3-Month PSG Follow-up] -> [12-Month PSG Follow-up] -> [Data Analysis] | +--> [Group B: OP-only] -> [Routine Follow-up] -----+

7. Safety Considerations

Participant safety is paramount. MFT is a non-invasive therapy with minimal risk.

- All surgical procedures will be performed by an experienced surgeon, and standard postoperative care protocols will be followed to manage potential complications such as pain or bleeding.
- The intensity of MFT exercises will be introduced gradually to prevent muscle strain.
- During all follow-up visits, researchers will actively monitor and record any adverse events related to either the surgery or the MFT. All adverse events will be reported to the Institutional Review Board (IRB) in accordance with regulations.

8. Data Management and Statistical Analysis

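### Section 7 records adverse events by judged relatedness yet promises to report all of them, and the relatedness test has two routes in Group A but one in Group B

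*Combined protocol and SAP*

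**What the plan says.** All references are to the combined protocol and SAP.

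- **Recording (section 7).** At follow-up visits "researchers will actively monitor and record any adverse events related to either the surgery or the MFT". This is the only recording rule in the document.
- **Reporting (section 7, next sentence).** "All adverse events will be reported to the Institutional Review Board (IRB) in accordance with regulations". Relatedness is not mentioned here.
- **Expected risk (section 7).** "MFT is a non-invasive therapy with minimal risk". For surgery, standard care is to "manage potential complications such as pain or bleeding"; muscle strain is foreseen for the exercises.
- **Who is exposed to what (section 6).** "All patients will undergo surgery performed by the same surgeon", so both groups have the surgical cause. MFT is given to Group A alone: "Group A patients will begin a 12-week MFT program starting at the third postoperative week".
- **Grouping (section 6).** "enrolled patients will be divided into two groups based on personal willingness".
- **Design (section 5).** "This is a prospective, single-surgeon, non-randomized controlled study conducted at a single medical center". No masking or independent assessor is mentioned there or elsewhere.
- **Analysis (sections 4, 6 and 8).** The objectives and listed outcomes are AHI, lowest oxygen saturation and snore index. Section 8 names no adverse event analysis.

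**The concern.** Whether an event has occurred and whether a treatment caused it are separate questions. Section 7 merges them, so the causal answer decides whether there is a record at all. It does not say who judges relatedness or by what criteria. Patients choose their group and MFT involves repeated therapist sessions, so the researchers will very probably know who is in which group. The same section has already described MFT as low in risk.

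The test is also not the same in the two groups. From the third postoperative week, a sore throat or a muscle complaint has two qualifying causes in Group A and one in Group B. Before that week no patient has started MFT, so only surgery can qualify in either group, yet nothing separates the two periods.

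At stake is the safety record, not the efficacy result. An event that was never written down cannot be recovered at analysis. The project aims to support MFT as part of routine postoperative care, so readers are likely to look at events by group even though no such comparison is planned.

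**Working it through.** The plan gives no adverse event rate, sample size or power for safety, so there is no figure to reproduce. The check is a reading of the text, followed by an illustration on assumed rates.

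**1. The two sentences side by side.** The recording sentence covers events related to surgery or MFT. The reporting sentence covers all events. If the first is applied literally, the second cannot be met for unrelated events. If the second governs, the qualifier in the first has no function. One of them has to change.

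**2. Qualifying causes.**

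| Period | Group A | Group B |
|---|---|---|
| Before the third postoperative week | surgery | surgery |
| From the third postoperative week | surgery or MFT | surgery |

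**3. How far attribution alone could move the counts.** Assumptions, none from the documents: both groups have the same true risk; *s* is the risk of a surgery-related event, recognised equally in both groups; *o* is the risk of any other event; *q* is the chance that such an event is called MFT-related in Group A.

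- True risk, both groups: s + (1 − s)·o
- Recorded in Group A: s + (1 − s)·o·q
- Recorded in Group B: s
- Artificial difference: (1 − s)·o·q

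Middle example, s = 0.20, o = 0.10, q = 0.5:

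- true risk 0.20 + 0.80 × 0.10 = 0.28 in both groups
- recorded in A 0.20 + 0.80 × 0.10 × 0.5 = 0.24
- recorded in B 0.20
- artificial difference 4 points; missed 4 points in A and 8 in B

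Over s = 0.10 to 0.30 and o = 0.05 to 0.20:

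| q | Smallest difference | Largest difference |
|---|---|---|
| 0 | 0 | 0 |
| 0.5 | 0.70 × 0.05 × 0.5 = 1.8 points | 0.90 × 0.20 × 0.5 = 9.0 points |
| 1 | 0.70 × 0.05 × 1 = 3.5 points | 0.90 × 0.20 × 1 = 18.0 points |

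**4. Would it show in a test?** Chance that the recorded difference reaches two-sided 0.05 with Group A higher (normal approximation, pooled variance under the null, assumed sizes). With no artificial difference it would be about 2.5%.

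| Patients per group | 24% v 20% | 36% v 20% (s = 0.20, o = 0.20, q = 1) |
|---|---|---|
| 20 | 4.9% | 19.9% |
| 30 | 5.6% | 27.8% |
| 50 | 7.0% | 42.8% |
| 100 | 10.1% | 71.5% |

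**5. Direction.** In this model the difference cannot favour Group A, because surgical events are assumed to be recognised equally. That may fail. If staff who regard MFT as harmless dismiss a mild complaint in Group A as ordinary exercise soreness, but record the same complaint in Group B as surgical, the sign reverses. The documents do not settle which is more likely.

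**6. Contact.** Section 6 gives Group A two training sessions plus biweekly reviews over 12 weeks: 2 + 12/2 = 8 contacts. Group B has routine follow-up with no stated frequency. If therapist contacts count as follow-up visits, detection is unequal as well.

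**7. After the change.** If every event is recorded, both groups record s + (1 − s)·o, and the artificial difference from attribution is 0.

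**The case against.** The strongest reply is that section 7 is a participant-protection paragraph, not an analysis plan. It does not say that unrelated events are discarded, its next sentence refers to all events, and section 9 commits the study to GCP. Pain is named as an expected surgical complication, so throat pain may well be recorded as surgical in both groups, where the asymmetry matters least. Grouping by willingness and a sample described only as modest would leave any comparison of adverse events confounded and imprecise even with perfect recording.

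Much of this stands, and it rules out several stronger readings that a reader might infer:

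- *That Group B cannot meet the recording rule.* It can: all patients have surgery. Only the MFT route is closed to Group B.
- *That unrelated events are certainly never recorded.* The text does not limit recording in so many words; that reading is an inference, and the reporting sentence pulls the other way.
- *That the researchers are known to be unmasked.* The documents are silent. It is a reasonable inference, not a stated fact.
- *That a planned safety comparison is biased.* None is planned.
- *That the wording alone prevents a test of the low-risk claim.* The non-randomised grouping and modest sample would limit that test anyway.

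What the reply does not remove is the mismatch. A general commitment to GCP does not tell staff which of the two sentences to follow when filling in an event form.

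**Conclusion.** The point holds in a limited form. Section 7 words recording by relatedness and reporting without it, and these must be reconciled. As worded, the causal judgement comes before the record, is made by researchers not described as masked, and has one more qualifying cause in Group A from the third postoperative week. Any adverse event counts by group would partly reflect attribution.

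The size is unknown. The 0 to 18 point range rests wholly on assumed rates, equal true risk and equal recognition of surgical events; it shows the mechanism and is not an estimate. The middle case of 4 points would seldom reach significance at 20 to 100 patients per group. The direction is also open. Efficacy conclusions are not affected. This is a cheap improvement that should be made, not a flaw that undermines the study.

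**What to change.** Replace the recording sentence in section 7 with wording to this effect: *All adverse events in both groups are recorded, whatever the suspected cause, with date of onset and severity. Relatedness to surgery or to MFT is assessed afterwards and entered as a separate field.* The reporting sentence then agrees with it.

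If events are shown by group:

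- separate those with onset before the third postoperative week from later ones;
- base the table on visits common to both groups, because Group A has extra therapist contacts;
- call the table descriptive, because grouping is by willingness and no safety comparison is planned.

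The cost is one rewritten sentence, one extra field on the event form and more minor events to log. No visit or treatment changes.

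Section 5 describes the project in the past tense, as running to January 2024. If data collection is already complete, unrecorded events cannot be recovered. The report should then state how events were collected and make no comparative safety claim.

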- **Data Management:** All research data will be de-identified and coded. The data will be entered into a password-protected electronic database accessible only to the research team.
- **Statistical Analysis:**
 - Continuous variables will be compared using paired or unpaired t-tests.
 - Categorical outcomes will be compared using the chi-square test.
 - A p-value of <0.05 will be considered statistically significant.

9. Quality Assurance

To ensure the quality and consistency of the study:

- All surgeries will be performed by a single surgeon to standardize the surgical technique.
- All MFT instruction and supervision will be conducted by the same speech-language pathologist to ensure consistency in the training protocol.

- All PSG data will be scored according to the standardized guidelines of the American Academy of Sleep Medicine.
- The study will be conducted in strict adherence to the IRB-approved protocol and Good Clinical Practice (GCP) guidelines.

10. Expected Outcomes of the Study

This study is expected to demonstrate that the addition of postoperative MFT significantly enhances the efficacy of surgical treatment for OSA. The findings will provide strong evidence for a multimodal treatment strategy, potentially influencing future clinical guidelines for OSA management. This research will advance the understanding of OSA pathophysiology by highlighting the importance of addressing both anatomical and neuromuscular functional deficits.

11. Dissemination of Results and Publication Policy

The results of the study will be submitted for publication in a peer-reviewed international medical journal. Authorship will be determined based on the contributions of each member of the research team, as detailed in the "Authors' contributions" section of the manuscript.

12. Duration of the Project

The total duration of the project is four years, from January 2020 to January 2024.

- Year 1: Patient recruitment, surgical interventions, and early postoperative follow-up.
- Years 2-3: Continued recruitment and completion of all 3-month and 12-month follow-up assessments.
- Year 4: Data compilation, statistical analysis, and manuscript preparation and submission.

13. Problems Anticipated

- **Problem:** The modest sample size may limit statistical power.
 - **Solution:** Future research could be designed as a larger, multi-center trial.
- **Problem:** The 12-month follow-up period does not capture long-term recurrence.

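### Patients choose their own group after surgery, yet every planned between-group test is unadjusted and self-selection is not listed as a limitation

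*Combined protocol and SAP*

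**What the plan says.** Section 5 describes the design openly: "This is a prospective, single-surgeon, non-randomized controlled study conducted at a single medical center". Section 6 (Grouping) says how the groups arise: "After surgery, enrolled patients will be divided into two groups based on personal willingness".

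The primary objective in Section 4 is "To compare the reduction in AHI at 3 and 12 months post-surgery between the OP+MFT and OP-only groups". The same objective also sets a binary criterion: "with success defined as >50% AHI reduction and a final AHI <20 events/hour". The secondary objectives compare change in LSaO₂ and snore index at the same times.

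Section 8 gives the whole analysis plan. For measurements it says: "Continuous variables will be compared using paired or unpaired t-tests". For success and other binary results it says: "Categorical outcomes will be compared using the chi-square test". A 0.05 threshold completes it. It has no covariate, matching, weighting, stratification or sensitivity analysis, and no other section supplies one. It does not say whether the t-test on AHI reduction uses absolute change, percentage change or the final value.

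Section 13 lists sample size, follow-up length and self-reported adherence as problems, but not self-selection. Section 10 nevertheless expects strong evidence for the combined treatment. The baseline values needed for adjustment will exist for everyone, because Section 6 states: "All participants will undergo overnight polysomnography (PSG) at the sleep center at baseline (pre-surgery), and at 3 and 12 months post-surgery".

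**The concern.** An unadjusted test answers the study question only if volunteers and decliners would have had the same results without MFT. Self-chosen groups give no assurance of that, for two reasons.

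- **Measured factors.** Eligibility limits BMI, tonsil size, palate position and, loosely, age. Baseline AHI has a floor of 15 and no ceiling, so the groups can differ widely on the variable that drives the primary outcome.
- **Unmeasured factors.** The choice comes after surgery, so motivation and early recovery can influence it.

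The undefined form of AHI reduction makes this worse. With the same baseline gap, the spurious difference can favour one group on absolute change and the other on final AHI. The larger trial that Section 13 suggests for the sample-size problem would not help here: with self-selected groups, more patients make a spurious difference more likely to reach significance.

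**Working it through.** The plan states no sample size, SD, effect size or baseline data, so it has no figure to reproduce. What follows shows scale only.

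**Assumed inputs (none from the documents):** baseline AHI SD 20 in both groups; error SD 10; follow-up AHI rising with baseline at a slope *b* of 0.3 to 0.6; a baseline gap *g* of 5 or 10/h; no MFT effect; *n* = 30 or 50 per group; two-sided 5% tests. Rejection rates come from the noncentral t distribution.

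**Formulas**

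- Absolute change: bias (1 − b) × g, in favour of the group with the higher baseline; SE = √(2 × [(1 − b)² × 400 + 100] / n).
- Final AHI: bias b × g, in the opposite direction; SE = √(2 × [b² × 400 + 100] / n).

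**Worked case, b = 0.4, g = 10**

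- Absolute change: bias 0.6 × 10 = 6.0/h. For n = 30, SE = √(2 × [0.36 × 400 + 100] / 30) = √(488/30) = 4.03, and 31% reject. For n = 50, SE = 3.12, and 48% reject.
- Final AHI: bias 0.4 × 10 = 4.0/h. For n = 30, SE = √(2 × [0.16 × 400 + 100] / 30) = √(328/30) = 3.31, and 22% reject. For n = 50, SE = 2.56, and 34% reject.

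**Range over b = 0.3 to 0.6**

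| Outcome tested | Gap | Bias | False positives, n = 30 | n = 50 |
|---|---|---|---|---|
| Absolute change | 5/h | 2.0–3.5/h | 9–12% | 12–17% |
| Absolute change | 10/h | 4–7/h | 22–34% | 34–52% |
| Final AHI | 5/h | 1.5–3.0/h | 8–11% | 10–16% |
| Final AHI | 10/h | 3–6/h | 17–31% | 25–48% |

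**Percentage change** (simulated, baseline means 61 and 51). The rate stays at 5% if the fall is strictly proportional to baseline. If follow-up = 8 + 0.3 × baseline, mean reductions are 55.5% and 51.9%. If follow-up = −8 + 0.5 × baseline, they are 64.6% and 68.1%. Both cases reject in about 9% (n = 30) or 12% (n = 50), in opposite directions.

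**Success.** Above a baseline of 40, the limit of 20 demands more than a 50% fall: (50 − 20)/50 = 60% at AHI 50, and (60 − 20)/60 = 67% at AHI 60. With slope 0.4 and a log-normal baseline truncated at 15, means of 61 and 51 give success rates of 36% and 46%, and chi-square rejects in 12% or 17%. Means of 45 and 35 give 50% and 55%, and it rejects in 6% or 8%.

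**With baseline AHI in the model**, simulated rejection rates were about 4–6% for AHI and 4–7% for success. This holds because baseline was the only confounder and was measured without error.

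**What adjustment cannot do.** Take an unmeasured factor worth *u* per hour and no baseline gap. The adjusted bias is still *u*, with SE √(200/n), which is 2.58 for n = 30 and 2.00 for n = 50. For u = 2, 3 and 5 the adjusted test rejects in 12%, 21% and 48% (n = 30) or 17%, 32% and 70% (n = 50). Being more precise, it flags the 5/h bias more often than the unadjusted test on absolute change, which rejects in 20–32% or 30–49% over the slope range (23% or 35% at slope 0.4).

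**The case against.** The plan does not conceal its design: it says that the study is non-randomized and that patients choose. One surgeon operates on everyone, and eligibility narrows the case mix. Nothing in the documents shows that an imbalance exists. The largest rates above need a gap of half the assumed SD; at 5/h they are modest. All of this is fair, and it limits how strongly the point can be put. But disclosing a design does not analyse its consequences, and none of these features balances baseline AHI.

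It can also be said that comparing change already deals with baseline. It does so only if follow-up AHI rises one-for-one with baseline.

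Four objections to the remedy stand in part:

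- The logistic model gains little in the milder scenario. For means 45 and 35, simulated rates were 6.1% unadjusted and 5.9% adjusted (n = 30), and 7.3% and 6.7% (n = 50). For means 61 and 51 the gain is clear: 11.8% to 5.4%, and 16.2% to 4.9%. In this illustration success also rises with baseline up to AHI 40 and then falls, so a single linear baseline term is only an approximation.
- Adjusting for each outcome's own baseline leaves age and BMI unadjusted, and Section 13 should not claim more.
- Section 8 refers to continuous variables generally, so a baseline comparison is not excluded, only not required.
- The document is dated January 2020, but Section 5 uses the past tense: "The project was conducted between January 2020 and January 2024". If outcomes are known, a new main analysis can no longer be prespecified.

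**Conclusion.** The concern holds. The groups are self-chosen after surgery, the only between-group tests are unadjusted, and self-selection is missing from the stated limitations. Followed as written, the plan can give a biased answer in either direction.

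The actual size and direction cannot be derived from the documents. Under the assumed inputs, false-positive rates for AHI run from about 8% to 52%, depending on gap, slope, group size and whether absolute change or final AHI is tested. The conclusion itself does not depend on those numbers. The part due to baseline AHI can be reduced cheaply; the part due to unmeasured factors cannot be removed by analysis and has to be acknowledged. This is a low-cost improvement, and it is no reason to reject the study.

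**What to change.** **Section 8.** Add, as the main between-group analysis at 3 and 12 months, a linear regression of follow-up AHI on group and baseline AHI. Do the same for LSaO₂ and snore index, each with its own baseline value. Analyse success by logistic regression on group and baseline AHI. With baseline in the model, absolute change and final AHI give the same group estimate and p-value, so that ambiguity disappears. Keep the planned t-tests and chi-square tests, report them alongside as unadjusted results, and state which form of reduction the t-test uses. Require a table of baseline values by group.

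**If outcome data have already been seen,** leave the planned tests in their place and label the adjusted analysis post hoc.

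**Section 13.** List self-selection. State that adjustment covers only each outcome's own baseline value, and that other differences, including motivation and early postoperative experience, can still bias the result.

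**Section 10.** Describe the expected finding as an adjusted association in self-selected patients.

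**Cost.** SAP wording and one covariate per outcome, taken from the baseline PSG already planned for every participant. The price is a more modest conclusion and, if outcomes are known, the post hoc label.

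### Section 8 leaves the scale of the AHI comparison undefined and without baseline adjustment; read by default as raw change, the t-test is inefficient for an outcome justified by a proportional effect

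*Combined protocol and SAP*

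**What the plan says.** The plan for continuous outcomes in section 8 is one sentence: "Continuous variables will be compared using paired or unpaired t-tests". The significance rule is "A p-value of <0.05 will be considered statistically significant"; sidedness is not stated. No transformation, skewness check, fallback test or covariate is named.

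The primary objective in section 4 is "To compare the reduction in AHI at 3 and 12 months post-surgery between the OP+MFT and OP-only groups". A responder rule is attached to it: "with success defined as >50% AHI reduction and a final AHI <20 events/hour". The success rule has one proportional part and one absolute part. As a yes/no outcome it falls under a different sentence of section 8: "Categorical outcomes will be compared using the chi-square test". Whether the continuous reduction is in events/hour or in percent of baseline is not stated.

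The rationale in section 3 is proportional: "A meta-analysis has already demonstrated that MFT alone can reduce the AHI by 50% in adults". Section 5 requires a baseline AHI of at least 15 and sets no upper limit. Section 13 concedes: "The modest sample size may limit statistical power". No sample size, SD, AHI distribution or power is given anywhere.

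**The concern.** AHI cannot go below zero and has no upper limit at entry, so a right-skewed distribution is likely. If MFT removes a fraction of the AHI that surgery leaves, its benefit in events/hour grows with baseline severity, and so does the scatter. A t-test on raw change then averages quantities of very different size against a variance inflated by the high-AHI patients. Without baseline adjustment, the spread of baseline severity also stays in the error term.

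The stake is power on the primary outcome of a study that already expects to have little of it. A second stake is that raw change, percent change and log ratio all remain open until the data are seen. The wording also permits a pooled-variance t-test, although the groups are self-chosen and may differ in size and spread.

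**Working it through.** The plan states no power or sample size, so there is no figure of its own to reproduce.

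**Inputs.** From the documents: baseline AHI of at least 15; a 50% reduction for MFT alone; average long-term surgical success of 30%; alpha 0.05 (two-sided assumed). Everything else is assumed. In the central case there are 30 per group; baseline AHI is log-normal with median 40 and log-SD 0.5, truncated to 15-120; surgery leaves a median 0.55 of baseline; MFT multiplies the remainder by 0.6; and the SD of the log ratio is 0.6. The ranges are median 35-45, log-SD 0.35-0.6, surgery ratio 0.45-0.55, MFT ratio 0.5-0.7 and SD of log ratio 0.6-0.8. Simulated surgery-alone success is then 31-52%.

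**Why scale matters.** MFT benefit = baseline × 0.55 × (1 − 0.6) = 0.22 × baseline. That is 3.3 events/h at baseline 15 and 17.6 at baseline 80. On the log scale it is ln 0.6 = −0.51 at every baseline.

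**Central case, proportional effect.** For 80% power, n per group = 2(1.96 + 0.8416)²(SD/Δ)² = 15.70 (SD/Δ)².
- Raw change, simulated Δ 11.4 and SD 19.1: 15.70 × 2.807 = 44.1, so 45.
- Log ratio, Δ 0.51 and SD 0.60: 15.70 × 1.384 = 21.7, so 22. The ratio is 45/22 = 2.05.
- Power at 30 per group = Φ(√15 × Δ/SD − 1.96). Raw: Φ(2.31 − 1.96) = 0.64. Log: Φ(3.29 − 1.96) = 0.91. Direct simulation gave 0.64 and 0.90.

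Over the ranges, raw change needs 36-86 per group and the log ratio 21-46, a factor of about 1.5 to 2.8. Power at 30 per group is 0.37-0.75 against 0.62-0.92.

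**Additive effect.** With a constant benefit of 8-10 events/h and normal error of SD 12-15, power at 30 per group is 0.45-0.74 for raw change, 0.53-0.75 for log ratio, 0.64-0.85 for percent change and 0.67-0.87 for raw AHI adjusted for baseline.

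**Scale or adjustment?** A second set (30 per group, baseline median 40, log-SD 0.5, at least 15, surgery ratio 0.4, proportional effect) gave:

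| MFT ratio, residual log-SD | Raw change | Percent change | Raw, adjusted | Log, adjusted |
|---|---|---|---|---|
| 0.7, 0.5 | 26% | 72% | 62% | 75% |
| 0.5, 0.8 | 51% | 81% | 74% | 91% |

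In the first row adjustment gives 62 − 26 = 36 of the 49 points and scale the other 13. In the second, adjustment gives 74 − 51 = 23 of 40 and scale 17. The split depends on the order of the steps: in the central-case model an unadjusted t-test on the log ratio (0.62-0.92) does as well as adjusted log AHI (0.61-0.91).

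With additive normal error instead (surgery ratio 0.55, SD 10-15, benefit 5-10 events/h), four scenarios gave 45, 85, 69 and 69% for adjusted raw AHI and 36, 74, 58 and 61% for adjusted log AHI. The raw scale leads by 9, 11, 11 and 8 points.

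**Wider set of assumed scenarios, 30 per group.** With multiplicative error, power was 20-90% for raw change and 37-100% for adjusted log(AHI+1). With additive error it was 13-70% and 20-92%, with adjusted raw AHI at 24-96%. Adjusted log AHI beat raw change in every scenario with a true effect. All methods had size of about 5%.

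**Unequal groups.** Take 15 v 45 with SD 1.5 v 1 (assumed). The true variance of the difference is 2.25/15 + 1/45 = 0.172. The pooled estimate is about [(14 × 2.25 + 44)/58] × (1/15 + 1/45) = 1.302 × 0.0889 = 0.116. The standard error is thus understated by a factor of √(0.116/0.172) = 0.82, and a critical value of 2.00 acts like 1.64, a size of about 10%. Simulation gave 10.3% for Student's t and 4.9% for Welch.

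**The case against.** Several stronger readings are tempting, and the documents do not support them.

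- A reader might infer that the plan has chosen the raw scale. It has not: raw change is the default reading of a t-test with no transformation named, but percent change is also permitted. Under percent change the loss is much smaller in one proportional scenario (72% against 75%) and moderate in another (81% against 91%).
- A reader might infer that a few severe non-responders dominate the variance. No AHI distribution is given. In the simulations such patients are 23-30% of the surgery-only arm and carry 35-52% of the variance of raw change, while patients with above-average reductions carry 32-53%.
- A reader might infer that the loss persists once raw AHI is adjusted for baseline. That holds with proportional effects and multiplicative error. With additive effects and errors the ranking reverses.
- The success rule is only half proportional and goes to a chi-square test, which extreme AHI values cannot drive. The 50% figure is for MFT alone, so it is not an expected added effect over surgery.
- The log scale changes what is estimated: on log(AHI+1), 1 v 4 events/h counts the same as 15 v 39, since 5/2 = 40/16 = 2.5.
- Self-selection is a larger threat than the choice of scale.

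All of this stands as a limit on the point. None of it defends leaving scale and adjustment unspecified. The unadjusted raw-change test lost to adjusted log AHI under both error models.

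**Conclusion.** The point holds in a limited form. Section 8 leaves the AHI scale undefined and provides only unadjusted t-tests. Under the default reading this wastes power in a study that describes itself as modest in size. The direction is consistent across the scenarios tried. The amount cannot be derived from the documents, because sample size, SD and added effect are all absent, and the wide power ranges reflect that.

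The case for the log scale over adjusted raw AHI rests on the protocol's proportional rationale: 13-17 points gained in the two proportional scenarios tabulated, against 8-11 points lost in the four additive ones. The case for baseline adjustment does not depend on that choice. With similar groups this is a matter of efficiency and pre-specification, not validity, since all methods held their size. The Welch or robust-variance part does concern validity if the smaller group is also the more variable one. No choice of scale removes confounding from patients choosing their own group.

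**What to change.** In section 8, replace the generic sentence, for AHI, with a pre-specified analysis:

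- The between-group comparison at 3 and at 12 months uses log(AHI+1), adjusted for log baseline AHI.
- The result is reported as an approximate ratio of geometric means (OP+MFT to OP) with a 95% CI.
- Robust standard errors are used in the adjusted model, and Welch's test wherever an unadjusted t-test is kept.
- The baseline-adjusted difference in events/hour is reported as a sensitivity analysis.

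In section 4, state whether the AHI reduction is absolute or relative, in line with this choice.

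The cost is a few lines of text and no new data. The downsides are that the headline is a ratio rather than events/hour, that the added constant makes the ratio approximate and gives weight to differences near zero, and that some power is lost against adjusted raw AHI if effects and errors are additive. Confounding from allocation by willingness needs separate treatment.
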